# 6.8. Concomitant Therapy

Any medication or vaccine, including OTC or prescription medicines, vitamins, and/or herbal supplements, that the participant is receiving at the time of enrollment or receives during the study must be recorded along with

- reason for use
- dates of administration including start and end dates, and
- dosage information including dose and frequency for concomitant therapy of special interest.

The medical monitor should be contacted if there are any questions regarding concomitant or prior therapy.

Participants on the following medications according to local practice must be on a stable regimen for at least 4 weeks prior to screening and expected to remain on a stable regimen through the end of the Treatment and Assessment Period, unless changes need to be made because of AEs:

- lipid-lowering drugs (such as statins, ezetimibe, PCSK9 inhibitors, prescription-dose niacin, fibrates, fish oil, or other products containing omega-3 fatty acids, including OTC preparations), and
- testosterone, estrogens, progesterone, growth hormone, or progestins.

# 7. Discontinuation of Study Intervention and Participant Discontinuation/Withdrawal

Discontinuation of specific sites or of the study as a whole are handled as part of Appendix 1 (Section 10.1).

## 7.1. Discontinuation of Study Intervention

When necessary, a participant may be permanently discontinued from study intervention. If so, the participant will remain in the study and follow procedures for remaining study visits, as shown in the SoA.

A participant should be permanently discontinued from study intervention if

- the participant becomes pregnant during the study
- in the opinion of the investigator, the participant should permanently discontinue the study intervention for safety reasons
- if the investigator determines that a systemic hypersensitivity reaction has occurred related to study intervention administration, the participant may be permanently discontinued from the study intervention, and the sponsor's designated medical monitor should be notified. If the investigator is uncertain about whether a systemic hypersensitivity reaction has occurred and whether discontinuation of study intervention is warranted, the investigator may consult the sponsor
- the participant has an AE or an SAE or a clinically significant change in a laboratory value that, in the opinion of the investigator, merits discontinuation of study intervention and appropriate measures being taken
- if the participant experiences a hepatic event or liver test abnormality as specified in the liver chemistry stopping criteria (see Section 7.1.1), and
- HBV or HCV: The participant tests positive for HBV DNA (see Section 8.2.4) or tests positive for HCV RNA (Section 8.2.5).

Note: The HBV DNA result is to be confirmed if initial positive test result is positive but below the level of quantification. Prior to discontinuation of any immunomodulatory and/or immunosuppressive therapy, including study intervention, the participant is to be referred to, evaluated, and managed by a specialist physician with expertise in evaluation and management of viral hepatitis. The timing of discontinuation from study intervention relative to the initiation of any antiviral treatment for hepatitis is to be based on the recommendation of the consulting specialist physician, in conjunction with the investigator, and aligned with medical guidelines and standard of care.

## 7.1.1. Liver Chemistry Stopping Criteria

#### Interrupting study drug based on liver test elevations in participants with normal or nearnormal baseline liver tests

In study participants with normal or near-normal baseline liver tests (ALT, AST, alkaline phosphatase [ALP] <1.5x ULN), the study drug should be **interrupted** or discontinued and close hepatic monitoring initiated (see Appendix 10.6) if one or more of these conditions occur:

Elevation	Exception
ALT or AST >8x ULN	
ALT or AST >5x ULN for more than 2 weeks	
ALT or AST >3x ULN and either TBL >2x ULN or INR >1.5	For participants with Gilbert's syndrome: If baseline direct bilirubin is >0.5 mg/dL, then doubling of direct bilirubin should be used for drug interruption decisions rather than TBL >2x ULN.
ALT or AST >3x ULN with the appearance of fatigue, nausea,	
vomiting, right upper quadrant pain or tenderness, fever, rash, and/or eosinophilia (>5%)	
ALP $>$ 3x ULN, when the source of increased ALP is the liver	
ALP >2.5x ULN and TBL >2x ULN	For participants with Gilbert's syndrome: If baseline direct bilirubin is $>0.5 \text{ mg/dL}$ , then doubling of direct bilirubin should be used for drug interruption decisions rather than TBL $>2x$ ULN.
ALP >2.5x ULN with the appearance of fatigue, nausea,	
vomiting, right upper quadrant pain or tenderness, fever, rash, and/or eosinophilia (>5%)	

Source: FDA Guidance for Industry: Drug-Induced Liver Injury: Premarketing Clinical Evaluation, July 2009 and other consensus guidelines, with minor modifications

Abbreviations: ALP = alkaline phosphatase; ALT = alanine aminotransferase; AST = aspartate aminotransferase; FDA = Food and Drug Administration; INR = international normalized ratio; TBL = total bilirubin; ULN= upper limit of normal.

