1.2. Schema

1.3. Schedule of Activities (SoA)

Period I - Optional Prescreening: The study includes an optional prescreening visit (Visit 601) as a simple way for sites to determine whether participants meet Lp(a) criteria, as assessed by a central laboratory assessment, before the full screening activities are initiated at Visit 1. If the participant has not had Lp(a) measured before or is unknown, the prescreening visit should be completed. The prescreening visit can be conducted at the study site, or remotely, for example, at a mobile healthcare or alternate laboratory. The prescreening activities will be described in an appropriate informed consent form (ICF). Informed consent for the prescreening activities will be obtained, a participant identification number will be assigned, and sample for the Lp(a) prescreening laboratory test will be obtained. The optional prescreening visit can be repeated 1 time (no more) per participant if the investigator believes the participant would meet criteria at a later time, with a minimum of 4 weeks between visits. Repeated sampling in the prescreening is opted for, central laboratory testing for Lp(a) is still required as part of the screening procedures conducted at Visit 1. Participants with Lp(a) <175 nmol/L at Visit 1 will not be eligible for enrollment, despite their values in prescreening. A prescreening visit occurring longer or shorter than 21 days (3 weeks) from screening will not be considered a protocol deviation.

Period II - Screening: Visit 1 procedures may be conducted over more than 1 day as long as all activities are completed prior to Visit 2.

Period III - Treatment and Assessment Period: All procedures (screening and baseline) need to be completed prior to the first dose of study intervention. For an early discontinuation (ED) from the study intervention that occurs before the last visit in treatment period, see the activities listed for ED in this table.

	Period I - Pre- Screening	Period II - Screening			Per	riod I	II T	reatm		Participants are required to fast before Visits 1-12. See Section 5.3.1. If a participant arrives not fasted, schedule the laboratory draw for another date.					
Visit number	601	1	2	3	4	5	6	7	8	9	10	11	12	ED	
Days from randomization	≤42	≤21		15	30	60	120	180	210	240	300	360	540		Visit 1 procedures may be conducted over more than 1 day if all activities are completed within the allowable visit tolerance.

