	Period I - Pre- Screening	Period II - Screening			Per	riod I	II T	reatm	Participants are required to fast before Visits 1-12. See Section 5.3.1. If a participant arrives not fasted, schedule the laboratory draw for another date.						
Visit number	601	1	2	3	4	5	6	7	8	9	10	11	12	ED	
Days from randomization	≤42	≤21		15	30	60	120	180	210	240	300	360	540		Visit 1 procedures may be conducted over more than 1 day if all activities are completed within the allowable visit tolerance.
Visit interval tolerance (days)	See Section 1.3	—		±3	±3	±3	±7	±7	±7	±7	±7	±7	±14		
Vital signs		Х	x	X	X	Х	х	х	х	х	х	х	х	х	Includes pulse rate and blood pressure measured after participant has been sitting at least 5 minutes and before ECG tracing and collection of blood samples for laboratory testing.
Physical examination		Х											х	Х	The physical examination is performed (excludes pelvic, rectal, and breast examinations unless clinically indicated).
Symptom- directed physical assessment								Х							Symptom-directed physical assessment will be conducted at the discretion of the PI or qualified personnel, per local regulations, as indicated based on participant status and standard of care.
12-Lead ECG (local)		Х						X				X	X	X	Collect single, local ECG prior to collection of blood samples for laboratory testing, including PK samples. Participants should be supine for approximately 5 to 10 minutes before ECG collections and remain supine but awake during the ECG collection. ECGs may be repeated at the PI's discretion at any visit. See Section 8.2.1.

	Period I - Pre- Screening	Period II - Screening			Pei	riod I	11 T	reatmo		Participants are required to fast before Visits 1-12. See Section 5.3.1. If a participant arrives not fasted, schedule the laboratory draw for another date.					
Visit number	601	1	2	3	4	5	6	7	8	9	10	11	12	ED	
Days from randomization	≤42	≤21	_	15	30	60	120	180	210	240	300	360	540		Visit 1 procedures may be conducted over more than 1 day if all activities are completed within the allowable visit tolerance.
Visit interval tolerance (days)	See Section 1.3			±3	±3	±3	±7	±7	±7	±7	±7	±7	±14		
Laboratory Tests and Sample Collections															
Hematology		Х			Х	Х		Х	Х	Х		Х	Х		
Clinical chemistry		Х	Х	Х	Х	Х		Х	Х	Х		Х	Х	Х	
Lipid panel		Х	Х			Х		Х		Х		Х	Х	Х	
Urinalysis		Х				Х		Х		Х		Х	Х	Х	
UACR		Х				Х		Х		Х		Х	Х	Х	
Serum pregnancy		Х													Females only.
FSH		Х													Optional; performed as needed to confirm postmenopausal status. See Appendix 10.4.

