TSH		Х													
HbA1c		Х						Х				Х	Х	Х	
Lp(a)	Х	Х	Х	Х	Х	Х	Х	Х	Х	Х	Х	Х	Х	Х	
ApoB		Х	Χ			Х	Х	Х	Χ	Х	Х	Х	Х	Х	
hsCRP		Х	Х			Х	Х	Х	Х	Х	Х	Х	Х	Х	
HIV screening test		Х													

	Period I - Pre- Screening	Period II - Screening			Per	riod I	II T	reatm		Participants are required to fast before Visits 1-12. See Section 5.3.1. If a participant arrives not fasted, schedule the laboratory draw for another date.					
Visit number	601	1	2	3	4	5	6	7	8	9	10	11	12	ED	
Days from randomization	≤42	≤21		15	30	60	120	180	210	240	300	360	540		Visit 1 procedures may be conducted over more than 1 day if all activities are completed within the allowable visit tolerance.
Visit interval tolerance (days)	See Section 1.3	—		±3	±3	±3	±7	±7	±7	±7	±7	±7	±14		
HCV screening test		Х													If HCV antibody test is positive, it must be followed by an HCV RNA test. See Section 8.2.5.
HBV screening test		Х													If HBsAg is negative and HBcAb is positive, further testing with HBV DNA is required. If the screening HBV DNA is negative, the participant is not excluded. See Section 8.2.4.
eGFR		Х				Х		Х		Х		Х	Х	Х	Calculated using CKD-EPI method.
Postdose PK sample			x					х							 Visit 2: Collect 2 samples. 0.5 hours postdose 4-9 hours postdose (minimum 2 hours) Visit 7: Collect 1 sample. 1. 24-36 hours postdose, will require participant to return 1 day after Visit 7.
Immunogenicity (ADA)			Р	Х	Х		Х	Р		Х		Х	Х	Х	Visit 2 and 7 will be collected predose.
PK sample for immunogenicity				X	X		X	Р		x		X	X	X	Collect a time-matched PK sample for all scheduled and unscheduled immunogenicity samples. Visit 7 will be collected predose.

	Period I - Pre- Screening	Period II - Screening			Per	iod II	(I T)	reatme		Participants are required to fast before Visits 1-12. See Section 5.3.1. If a participant arrives not fasted, schedule the laboratory draw for another date.					
Visit number	601	1	2	3	4	5	6	7	8	9	10	11	12	ED	
Days from randomization	≤42	≤21		15	30	60	120	180	210	240	300	360	540		Visit 1 procedures may be conducted over more than 1 day if all activities are completed within the allowable visit tolerance.
Visit interval tolerance (days)	See Section 1.3	—		±3	±3	±3	±7	±7	±7	±7	±7	±7	±14		
Stored Samples (On dosing days, collect samples before dosing	
Optional genetics sample			X												Sample can be obtained at or after the specified visit. See Appendix 10.5.
Exploratory biomarker samples			X			X		Х		Х		Х	х		
Randomization and Dosing															

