Register visit with IWRS		X	X	X	X	X	X	Х	Х	Х	Х	Х	Х	Х	Unscheduled visits are not required to be registered in IWRS.
Randomization via IWRS			X												
Dispense study intervention via IWRS			X					X							
Administer study intervention			X					Х							

Abbreviations: ACC/AHA = American College of Cardiology/American Heart Association; ADA = anti-drug antibody; AE = adverse event; ApoB = apolipoprotein b; ASCVD = atherosclerotic cardiovascular disease; CAD = coronary artery disease; CKD-EPI = Chronic Kidney Disease Epidemiology Collaboration; DNA = deoxyribonucleic acid; ECG = electrocardiogram; ED = early discontinuation; eGFR = estimated glomerular filtration rate; FSH = follicle-stimulating hormone; HbA1c = hemoglobin A1c; HBcAb = hepatitis B core antibody; HBsAg = hepatitis B surface antigen; HBV = hepatitis B virus; HCV = hepatitis C virus; HIV = human immunodeficiency virus; hsCRP = high-sensitivity C-reactive protein; ICF = informed consent form; IWRS = Interactive Web-Response System; Lp(a) = Lipoprotein(a); P = predose; PI = principal investigator; PK = pharmacokinetic; RNA = ribonucleic acid; TSH = thyroid stimulating hormone; UACR = urine albumin creatinine ratio.

2. Introduction

LY3819469 is a novel Dicer-substrate small interfering ribonucleic acid (siRNA) oligonucleotide designed to reduce the levels of *LPA* mRNA and apolipoprotein(a) (Apo[a]) expression and thereby to decrease lipoprotein(a) (Lp[a]). LY3819469 is being developed to reduce the risk of cardiovascular events in patients with or at high risk of atherosclerotic cardiovascular disease (ASCVD) and high levels of Lp(a)

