2.2.4. Introduction to LY3819469

LY3819469 inhibits the production of Apo(a) by causing degradation of LPA mRNA through the siRNA mechanism. LY3819469 reduces steady-state levels of Apo(a) protein in a mouse model transgenic for human Apo(a), and Lp(a) in cynomolgus monkeys that endogenously express Lp(a).

Nonclinical toxicology studies of LY3819469 showed no notable adverse drug effects.

In Phase 1 Study EZEA of participants treated with single LY3819469 doses up to 608 mg, Lp(a) was lowered and no notable adverse drug effects were observed.

Efficacy will be determined by measuring circulating levels of Lp(a) in this Phase 2 study to enable dose selection for Phase 3 study.

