4.1. Overall Design

Study EZEB is a parallel, double-blinded, placebo-controlled, dose-finding, Phase 2 study of LY3819469 in participants with elevated Lp(a).

Approximately 254 participants will be randomized in a 1:2:2:2:2 ratio to 1 of the following arms:

- Arm A: 16-mg LY3819469 dosed at randomization and Day 180
- Arm B: 96-mg LY3819469 dosed at randomization and Day 180
- Arm C: 400-mg LY3819469 dosed at randomization and Day 180
- Arm D: 400-mg LY3819469 dosed at randomization, and placebo at Day 180
- Arm E: placebo doses at randomization and Day 180

Treatment periods and assessments are described in the Schedule of Activities (SoA) (Section 1.3)

The study schema is shown in Section 1.2.

The study population is described in Section 5.

The efficacy and safety assessments are described in Sections 8.1 and 8.2, respectively.

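### No chemistry is scheduled between Day 60 and the Day 180 injection, so for a new rise scheduled data cannot meet the two-week liver stopping criteria in time

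*Protocol*

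**What the plan says.** **Stopping criteria.** Protocol 7.1.1 has one table for normal or near-normal baseline liver tests and one for abnormal baselines. Each has a single criterion that needs duration. In the first it is "ALT or AST >5x ULN for more than 2 weeks"; in the second it is ALT or AST above 3x baseline for the same length of time. The other criteria can be met at one visit: ALT or AST above 8x ULN (4x baseline), or lower rises combined with bilirubin, INR, symptoms or eosinophilia, and the ALP criteria.

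**Schedule.** In SoA 1.3 the row "Clinical chemistry" is marked at Visits 1 to 5 (up to Day 60), blank at Visit 6 (Day 120), and marked again at Visits 7 (Day 180) and 8 (Day 210). At Visit 6 blood is drawn for Lp(a), ApoB, hsCRP, ADA and the matched PK sample.

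**Dosing.** The row "Administer study intervention" is marked at Visits 2 and 7 only. Arms A, B and C receive active drug at both. Section 4.1 gives "Arm D: 400-mg LY3819469 dosed at randomization, and placebo at Day 180", and Arm E receives placebo throughout.

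**Order of events at Visit 7.** The SoA text says "All procedures (screening and baseline) need to be completed prior to the first dose of study intervention" and has no equivalent for the second dose. The ADA row says "Visit 2 and 7 will be collected predose", its PK sample is predose at Visit 7, and the stored-samples heading says "On dosing days, collect samples before dosing". The chemistry row has no such note. Section 8.2.2 requires laboratory results to be reviewed but sets no time relative to dosing. Appendix 2 calls for a local result when the central one will be too late for administering drug, and requires a local result used for that decision to be recorded.

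**The concern.** A stopping rule is useful only while there is a dose left to stop. There are two injections, so after the first one 7.1.1 governs a single decision: whether to inject at Day 180. An injection cannot be taken back.

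For a rise that begins after the Day 60 sample, Visit 7 gives the first scheduled chemistry value, on the day of that decision. The two-week criteria cannot be met from one value. Visits 7 and 8 together could show the duration, but by then no injection remains. The follow-up testing in 8.2.3 would supply the missing values, but it starts only once an elevation has been found, and no scheduled test can find one between Day 60 and Visit 7.

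**Working it through.** The plan states no figure for this gap, so there is none to reproduce. The group sizes used below do reproduce: 254/9 = 28.2 and 28.2 × 0.85 = 24.0 for the 16-mg arm; 2 × 28.2 = 56.4 and 56.4 × 0.85 = 47.9 for each other arm. These match the 24 and 48 completers in Protocol 9.5.

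**1. Visit windows (SoA 1.3).** Visit 5: Day 60 ± 3 = 57 to 63. Visit 6: Day 120 ± 7 = 113 to 127. Visit 7: Day 180 ± 7 = 173 to 187. Visit 8: Day 210 ± 7 = 203 to 217.

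**2. Gaps between chemistry samples.** Shortest gap = earliest later visit minus latest earlier visit; longest gap = the reverse.

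| Interval | Nominal | Shortest | Longest |
|---|---|---|---|
| Visit 5 to 7 (as planned) | 180 − 60 = 120 | 173 − 63 = 110 | 187 − 57 = 130 |
| Visit 7 to 8 (as planned) | 210 − 180 = 30 | 203 − 187 = 16 | 217 − 173 = 44 |
| Visit 5 to 6 (if added) | 120 − 60 = 60 | 113 − 63 = 50 | 127 − 57 = 70 |
| Visit 6 to 7 (if added) | 180 − 120 = 60 | 173 − 127 = 46 | 187 − 113 = 74 |

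**3. Can duration be shown in time?** Showing more than 14 days needs two elevated values more than 14 days apart. For a new rise after Day 60, the scheduled values available by the Day 180 injection number at most one (Visit 7), so the answer is no. Visits 7 and 8 are always at least 16 days apart and could show it, but after the last injection.

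**4. With chemistry at Visit 6.** At least 46 days remain before Visit 7. Subtracting 14 leaves about 32 days for central turnaround and for the 8.2.3 repeats (first at 48 to 72 hours, then one to three times weekly if the abnormality persists or worsens).

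**5. Residual case.** With a normal or near-normal baseline, the rise is above 5x but not above 8x ULN. With an abnormal baseline it is above 3x but not above 4x baseline. Exclusion criterion 26 admits ALT or AST up to 3x ULN. So the second band runs from 4.5x to 6x ULN at a baseline of 1.5x ULN, and from 9x to 12x ULN at a baseline of 3x ULN. In both cases no bilirubin, INR, ALP, symptom or eosinophilia criterion is met.

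**6. Who receives an active second dose.** Arms A to C: (1 + 2 + 2)/9 × 254 = 141, or 24 + 48 + 48 = 120 completers. Arms D and E receive placebo: 4/9 × 254 = 113.

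**7. Share of new rises that Visit 6 would catch first.** This rests on an assumption that is not in the documents: onset equally likely on any day between Visits 5 and 7, and the rise lasting to the next sample. Then 60/120 = 50%. Across windows it is (113 − 63)/(187 − 63) = 40% to (127 − 57)/(173 − 57) = 60%. Earlier onset would raise the share and later onset would lower it.

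**The case against.** The strongest reply is that a two-week rule is meant to be applied through follow-up testing, not from the visit schedule. Section 8.2.3 provides that testing, and it also calls for a comprehensive evaluation at 5x ULN or above (3x baseline or above), which covers the residual case. Section 8 directs that immediate safety concerns be discussed with the sponsor to decide whether drug continues. Section 7.1 lets the investigator stop drug for a laboratory change. Hematology is scheduled at Visit 7, so a lower rise with eosinophilia already meets a single-visit criterion. Concentrating chemistry in the 60 days after each dose is a defensible choice, and Protocol 2.2.4 reports that in Phase 1 "no notable adverse drug effects were observed".

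Most of this stands, and it is why the effect is modest. It does not close the gap, because 8.2.3 needs a first abnormal result and none can come from the schedule between Day 60 and Visit 7. The Phase 1 data come from single doses and do not address a second one.

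A reader might infer more than the documents support, in three ways:

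- That the second dose is given without any liver result. Appendix 2 anticipates a result before administration, and draw order may be set in the laboratory manual, which is not among the documents. What can be said is that the SoA does not mark the sample predose and that neither the SoA nor 7.1.1 points to Appendix 2.
- That the two-week criteria can never work before Day 180. Rises found at Days 15 to 60 are followed under 8.2.3, and unscheduled or symptom-driven tests remain possible.
- That any single value above 5x ULN at Visit 7 should hold the dose. That would be a new stopping rule without a release criterion, and it would have to be reconciled with the resumption conditions in 7.1.1.

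**Conclusion.** The point holds as a modest gap that is cheap to close. For a new rise after Day 60, scheduled chemistry cannot meet either two-week criterion before the only injection those criteria can withhold. The gap is 120 days nominal (110 to 130).

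The consequence is confined to the band in step 5. If such a rise is detected at Visit 7, the decision passes to 8.2.3, Section 8 and 7.1 rather than to the two-week criterion. If no result is in hand at the injection, the latest scheduled value is the one from Day 60. The figure of about 141 participants counts everyone assigned an active second dose; it is not an estimate of those affected. That number cannot be derived, because the documents give neither the rate of late liver rises nor the central laboratory's turnaround. The conclusion rests on the SoA marks as printed and on scheduled samples only.

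**What to change.** 1. **Mark clinical chemistry at Visit 6 (Day 120).** A rise found there starts 8.2.3 monitoring, and its duration can be established before Day 180. The longest scheduled gap before the second injection falls from 120 to 60 days nominal (46 to 74 from Visit 6 to Visit 7). The cost is one extra tube per participant at an existing draw, about 216 (24 + 4 × 48 completers) to 254 tubes. Rises that start after Day 120 are not covered and depend on item 2.

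2. **Mark Visit 7 chemistry as predose, and state that a current liver panel is reviewed against 7.1.1 before injection.** The panel may be central, or local under Appendix 2, with a cross-reference from the SoA and 7.1.1. A value above 5x ULN (3x baseline if baseline is abnormal) should go to the medical monitor before dosing, under Section 8 and 8.2.3. Any dosing after an interruption should follow the resumption conditions already in 7.1.1. The cost is a local panel wherever the central result is late: from none to about 216 to 254 panels, because turnaround is not stated and the blind needs the same step in every arm.

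Neither item adds a visit or changes an endpoint, the sample size or a stopping threshold.

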A similar estimand as the estimand for the primary objective will be used for the secondary objectives.

Unless specified otherwise, safety assessments will be guided by an estimand comparing safety of LY3819469 doses with placebo irrespective of adherence to study intervention.

Overall Design

Study is a parallel, double-blinded, placebo-controlled, dose-finding, Phase 2 study of LY3819469 in participants with elevated Lp(a).

Approximately 254 participants will be randomized in a 1:2:2:2:2 ratio to 1 of the following arms:

- Arm A: 16-mg LY3819469, doses at randomization and Day 180
- Arm B: 96-mg LY3819469, doses at randomization and Day 180
- Arm C: 400-mg LY3819469, doses at randomization and Day 180
- Arm D: 400-mg LY3819469, dosed at randomization, placebo at Day 180
- Arm E: placebo, doses at randomization and Day 180

Brief Summary:

The purpose of this study is to measure difference in percent change from baseline in timeaveraged Lp(a) on over Days 60-180 with LY3819469 versus placebo in participants with elevated Lp(a).

Study details include:

- The study duration will be up to 20 months.
- The treatment duration will include doses at the randomization visit and at Day 180.

Study Population:

The study will include adults at least 40 years old. People in the study who are on particular medicines should stay on the same doses for the whole study. People who have had a major illness or surgery in the 3 months prior to the study will not participate. People who have certain abnormal laboratory values will not be included.

Number of Participants:

Approximately 254 participants will be randomly assigned to study intervention.

Intervention Groups and Duration:

All participants will receive a subcutaneous injection at the randomization visit and at Day 180 (Visit 7). LY3819469 is formulated at a concentration of 160 mg/mL.

	Arm A	Arm B	Arm C	Arm D	Arm E
Intervention Name	LY3819469	LY3819469	LY3819469	LY3819469 and Placebo	Placebo ^a
Dosage #1					
LY3819469 Solution (160mg/mL)	16 mg (0.1 mL)	96 mg (0.6 mL)	400 mg (2.5 mL)	400 mg (2.5 mL)	_
Placebo (0.9% sodium chloride solution for injection)	_	_	_	_	Placebo ^a
Dosage #2					
LY3819469 Solution (160mg/mL)	16 mg (0.1 mL)	96 mg (0.6 mL)	400 mg (2.5 mL)	_	_
Placebo (0.9% sodium chloride solution for injection)	_	_	_	Placebo ^b	Placebo ^a
Route of Administration	SC injection	SC injection	SC injection	SC injection	SC injection

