# Interrupting study drug based on elevated liver tests in participants with abnormal baseline liver tests

In study participants with abnormal baseline liver tests (ALT, AST, ALP  $\geq 1.5x$  ULN), the study drug should be **interrupted** or discontinued if one or more of these conditions occur:

Elevation	Exception
ALT or AST >4x baseline	
ALT or AST >3x baseline for more than 2 weeks	
ALT or AST >2x baseline and either TBL >2x ULN or INR >1.5	For participants with Gilbert's syndrome: If baseline direct bilirubin is $>0.5$ mg/dL, then doubling of direct bilirubin should be used for drug interruption decisions rather than TBL $>2x$ ULN.
ALT or AST >2x baseline with the appearance of fatigue, nausea, vomiting, right upper quadrant pain or tenderness, fever, rash, and/or eosinophilia (>5%)	
ALP >2.5x baseline, when the source of increased ALP is the liver	
ALP >2x baseline and TBL >2x ULN	For participants with Gilbert's syndrome: If baseline direct bilirubin is >0.5 mg/dL, then doubling of direct bilirubin should be used for drug interruption decisions rather than TBL >2x ULN.
ALP >2x baseline with the appearance of fatigue, nausea, vomiting, right upper quadrant pain or tenderness, fever, rash, and/or eosinophilia (>5%)	

Source: FDA Guidance for Industry: Drug-Induced Liver Injury: Premarketing Clinical Evaluation, July 2009 and other consensus guidelines, with minor modifications

Abbreviations: ALP = alkaline phosphatase; ALT = alanine aminotransferase; AST = aspartate aminotransferase; FDA = Food and Drug Administration; INR = international normalized ratio; TBL = total bilirubin; ULN= upper limit of normal.

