#### Resuming study drug after elevated liver tests

Resumption of the study drug can be considered only in consultation with the Lilly-designated medical monitor and only if the liver test results return to baseline and if a self-limited nondrug etiology is identified. Otherwise, the study drug should be discontinued.

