# 9.5. Sample Size Determination

Approximately 254 participants will be randomly assigned in a 1:2:2:2:2 ratio to LY3819469 16 mg 2 doses: 96 mg 2 doses: 400 mg 2 doses: 400 mg 1 dose and placebo 1 dose:placebo 2 doses. Assuming a 15% dropout rate, this results in approximately 24 completers for the 16-mg group and 48 completers per arm for the rest of the groups.

Assuming a standard deviation of 20%, and a 2-sided alpha level of 0.05, the completers for each treatment arm will provide >99% power to detect a treatment difference of 70% reduction for the primary endpoint of LY3819469 versus placebo. The sample size was determined appropriate to provide a sufficient amount of safety data.

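### PT-INR is not explicitly required across part of the ALT/AST range in which INR >1.5 is a stopping criterion

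*Protocol*

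**What the plan says.** Protocol Section 7.1.1 has two tables of conditions for interrupting or discontinuing study drug. With near-normal baseline liver tests (below 1.5x ULN), one condition is "ALT or AST >3x ULN and either TBL >2x ULN or INR >1.5". With abnormal baseline tests (1.5x ULN or higher), the matching condition is "ALT or AST >2x baseline and either TBL >2x ULN or INR >1.5". Once drug has been interrupted, it may be resumed only in consultation with the medical monitor and "only if the liver test results return to baseline and if a self-limited nondrug etiology is identified".

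Where INR would come from is set out elsewhere in the protocol:

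- **Schedule of Activities and Appendix 2.** No row or panel contains PT-INR.
- **Section 8.2.3, close monitoring.** This starts at ALT/AST of at least 3x ULN, or at least 2x baseline if the baseline was abnormal. The repeat at 48 to 72 hours names ALT, AST, ALP, total and direct bilirubin, GGT and CK. Later monitoring names ALT, AST, ALP and TBL. If the abnormality persists or worsens, the stated minimum is a physical examination and history, in consultation with the medical monitor.
- **Section 8.2.3, comprehensive evaluation.** PT-INR is part of the stated minimum. Without symptoms, the ALT/AST trigger is 5x ULN or 3x baseline. With symptoms it is 3x ULN or 2x baseline. TBL and ALP have triggers of their own.
- **Appendix 10.6.** PT-INR is listed among the tests the central laboratory can run. For test selection the appendix points to Section 8.2.4, which covers hepatitis B.

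On dosing, the Synopsis states: "The treatment duration will include doses at the randomization visit and at Day 180".

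**The concern.** A stopping criterion works only if the value it depends on is measured. INR is an alternative to bilirubin here, so it adds something only when the bilirubin limb is not met. With a near-normal baseline TBL (and no Gilbert's syndrome), TBL at 2x ULN triggers the comprehensive evaluation by itself, and PT-INR with it. INR is therefore explicitly required once bilirubin has already settled the matter. It is not explicitly required in part of the range where INR alone would decide.

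At stake is a participant with raised transaminases and INR >1.5 whose stopping condition is met but not recognised. This criterion would then not bring the resumption conditions into play before the Day 180 dose.

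**Working it through.** The plan states no figure on this point, so there is none to reproduce. The check compares the range in which INR can decide stopping with the range in which PT-INR is required. It takes a participant with no hepatic symptoms and with TBL and ALP below the comprehensive-evaluation triggers.

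**Near-normal baseline (multiples of ULN)**

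| ALT or AST | Can INR >1.5 decide stopping (7.1.1)? | Is PT-INR explicitly required (8.2.3)? |
|---|---|---|
| >3x to <5x | Yes | No |
| 5x to 8x | Yes, unless >5x has lasted more than 2 weeks, which stops drug by itself | Yes |
| >8x | No, drug stops regardless | Yes |

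**Abnormal baseline (multiples of the participant's baseline)**

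| ALT or AST | Can INR >1.5 decide stopping (7.1.1)? | Is PT-INR explicitly required (8.2.3)? |
|---|---|---|
| >2x to <3x | Yes | No |
| 3x to 4x | Yes, unless >3x has lasted more than 2 weeks, which stops drug by itself | Yes |
| >4x | No, drug stops regardless | Yes |

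Stepping ALT/AST in hundredths gives the same result: the uncovered values run from 3.01 to 4.99x ULN and from 2.01 to 2.99x baseline. No other ALT/AST stopping condition applies inside either band. With hepatic symptoms both bands are empty, because the comprehensive evaluation then starts at 3x ULN or 2x baseline.

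**The second band in ULN terms.** Exclusion 26b admits ALT/AST up to 3.0x ULN. For a baseline of 2.5x ULN, the band runs from 2 × 2.5 = 5x ULN to 3 × 2.5 = 7.5x ULN.

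**Doses the rule can affect.** There are two dosing occasions. The first dose has already been given when any post-dose elevation is found, so the rule can withhold 1 of 2 doses, the one at Day 180. That dose is active drug in Arms A, B and C. It is placebo in Arm E and in Arm D ("Arm D: 400-mg LY3819469, dosed at randomization, placebo at Day 180"), where withholding it prevents no drug exposure.

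**The case against.** The strongest reply is that the documents already lead a site to INR. The close-monitoring list opens with the word *including* and cites Appendix 10.6, which contains a coagulation panel with PT-INR. Appendix 2 permits additional tests whenever the investigator finds them necessary. SAP Section 4.8.7.1.1 counts INR among the hepatic laboratory tests. A stopping rule that names INR is itself a prompt to check it. Section 7.1 also lets the investigator stop drug for safety reasons or for a clinically significant laboratory change, and Section 8 sends immediate safety concerns to the sponsor. Neither route needs an INR.

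Most of this stands, and it is why the effect is small. It does not close the gap. Appendix 10.6 is a menu that also lists hepatitis E serology and immunoglobulins, and its selection pointer leads to the wrong section. Medical-monitor consultation under Section 8.2.3 applies only if the abnormality persists or worsens, and INR is not specified even then. Discretion permits the test without requiring it.

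A reader might infer more than the documents support in three places:

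- **A long unmonitored interval.** The "Clinical chemistry" row has entries at Days 15, 30 and 60 and none at Day 120, which leaves 180 − 60 = 120 days before the second dose. That does not measure this gap. An elevation found by Day 60 leads to the 48 to 72 hour repeat and, if it persists or worsens, to monitoring at first 1 to 3 times weekly. An elevation that nobody detects would prompt no INR under any rule triggered by ALT/AST.
- **A large exposed group.** Arms A to C make up 5/9 of 254, about 141 participants. That is everyone due an active second dose, not the number who would fall in the bands with INR >1.5.
- **A need to exempt anticoagulant users.** Anticoagulants are not excluded, and the only exception in the 7.1.1 tables is for Gilbert's syndrome. But the documents give no figure for anticoagulant use, and no baseline INR is scheduled by which to judge an anticoagulant explanation. The criterion also requires raised transaminases and allows interruption with possible resumption. An exemption would loosen a cautious rule, and that is a trade-off, not a correction.

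**Conclusion.** The point holds in a narrow form. A site that follows the protocol exactly need not measure INR at >3x to <5x ULN, or >2x to <3x baseline, in a participant without symptoms whose TBL and ALP are below the comprehensive-evaluation triggers. Within those bands INR >1.5 would by itself meet the stopping rule.

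The consequence is small. It bears only on the Day 180 dose, and on drug exposure only in Arms A to C. To be affected, a participant must have an elevation found before that dose, fall in the band, have INR >1.5, and not have been stopped by the investigator on other grounds. The documents do not give the number who would meet all of these. That it is very small is a judgement, not a calculation. No efficacy analysis depends on INR, and neither do the hepatic summaries in SAP Table EZEB.4.7.

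A reader might conclude that the INR criterion cannot be applied at all. The documents do not support that: PT-INR is available centrally, required at the higher elevations and open to investigators at any time. This is a cheap improvement to a safety procedure.

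**What to change.** 1. In Section 8.2.3, name PT-INR among the 48 to 72 hour tests when ALT/AST is at least 3x ULN (near-normal baseline) or at least 2x baseline (abnormal baseline). These are the existing close-monitoring triggers, so the test is requested as soon as the INR alternative can apply.
2. In Appendix 10.6, change the test-selection pointer from Section 8.2.4 to Section 8.2.3. By itself this is clerical.

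The cost is a short wording change and one extra test, already offered by the central laboratory, on a repeat draw the protocol already requires. The downside is a few additional INR tests and an occasional raised INR to interpret. Leave the 7.1.1 tables as they are.
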